2.3.2 Known Potential Benefits

The study offers significant benefits to participants and to society, both of which have enabled highly successful recruitment into our prior similar studies. The direct benefits from participation in the study is undergoing opioid detoxification, receiving relapse prevention treatment for OUD, referral for continued treatment of OUD and incidental clinically relevant findings identified from the psychiatric, neuropsychological, and/or brain MRI procedures conducted during the study. There is also a strong benefit to society from understanding mechanisms that could potentially alter the way we treat opioid dependence and overdose.

Participant Retention: Participants will have numerous motives to remain in the study. First are the significant benefits of participation described in the previous section. Second, they will receive significant monetary compensation for their time. Third, the study team includes experienced clinicians who will make all efforts to create rapport with participants that will help them maintain contact even if they decided to end their pharmacotherapy. Last, the study coordinator and technician have been specially trained to maintain ongoing contact with OUD patients.

Protection of Participants: All medical records and research information will be kept confidential. Medical records, and research data may only be accessed by staff engaged in the research project or clinical care of the subjects, or by representatives of the National Institute on Drug Abuse, the Food and Drug Administration, or other government agencies as required and permitted by law. Prior to every session subjects will be reminded that should they become uncomfortable for any reason, the study can be terminated with no penalties. Participation will not have any effect on subject's legal status or medical care.

2.3.3 Assessment of Potential Risks and Benefits

Rationale for the necessity of exposing participants to risks and a summary of the ways that risks to participants were minimized in the study design: The project involves two medications that have been FDA approved for OUD in US and are in active clinical use in the US (Vivitrol, XRNTX) and Brixadi will be available on market by September 2023. Active ingredients of both medications are off patent medications that have been used for OUD for over 30 years in the US. Dosages, risks and benefits of both medications are well known in the literature and have been described in detail in Sections **2.2.1, 2.2.2, and 2.2.3**. They are both among the safest medications in their class and their use clearly outweighs the risks entailed in not providing these treatments to patients with OUD, first and foremost fatal opioid overdose, spread of infections such as HIV and Hepatitis C and criminal activity. Risks are minimized by inclusion and exclusion criteria that ensure enrollment of only participants with OUD and excluding all categories of patients at above usual risk of AE from either medication.

Justification as to why the benefits of participation in the study outweigh the risks of the information to be gained: Participation in the study benefits the participant directly as follows:

Directly to the participant: Free expert evaluation and initiation of state-of-the-art treatment for OUD and monitoring of its effects. Both medications are among the safest medications in their class and their use clearly outweighs the risks entailed in not providing these treatments to patients with OUD, first and foremost fatal opioid overdose, spread of infections such as HIV and Hepatitis C and criminal activity.

Benefit to society: as detailed in section 2.1 (Study Rationale), investigation of brain and behavioral mechanisms of the effects of the two injectable extended release preparations for the treatment of opioid use disorder with the ultimate goal of improving treatment outcomes in opioid use disorder.

3 STUDY OBJECTIVES AND ENDPOINTS

[figure not shown]
3.1 General Design

Study Design: The proposed study is a prospective open label 2-group study to compare the brain and behavioral responses of individuals with OUD receiving XRBUP and XRNTX treatments. The study will be conducted in two phases – Phase 1 = feasibility and Phase 2 = confirmation. Study interventions (XRNTX and XRBUP) and their duration will be same in both phases. Phase 1 (2 years) will have more cognitive and behavioral probes, some of which may not survive into Phase 2 (3 years) if found to not yield significant discrimination between the study interventions (groups). Participants will be men and women with current DSM-5 diagnoses of opioid use disorder (OUD) who will be randomized to XRBUP or XRNTX. Phase 1 will recruit 60 participants and Phase 2 will recruit 200 participants. The study length for each participant is comprised of up to 30 days of screening and baseline evaluations (called “week 1”), a 12-week open label trial (medication phase), and one follow-up visit 4 weeks after end of medication phase. The overall duration of the project will be 5 years (60 months). We intend to recruit 4 subjects per month for 40 months.

Table 1. Study timeline

Year/Phase	Year 1 (Phase 1)				Year 2 (Phase 1)				Year 3 (Phase 2)				Year 4 (Phase 2)				Year 5 (Phase 2)			
Quarter	Q1	Q2	Q3	Q4																
Preparation	X	X	X	X					X	X										
Recruitment		X	X	X	X	X	X	X	X	X	X	X	X	X	X	X	X			
Data Collection		X	X	X	X	X	X	X	X	X	X	X	X	X	X	X	X			
Data Analysis/QC			X	X	X	X	X	X	X	X	X	X	X	X	X	X	X	X	X	X
Publication				X	X			X	X			X	X			X	X	X	X	X

Figure 1: Outline of study interventions

3.2 Primary Study Endpoints (see Table in the Schedule of Activities (SoA), [Appendix Section 12.1](#)).

Clinical:

- 1) percent of the urine drug screen (UDS) tests positive for opioids during the last month of participation.
- 2) The number of study interventions (1,2 or 3) participant adhered to.

Surrogate: Brain fMRI response in three cognitive domains:

- 1) Response inhibition (Go-NoGo task)
- 2) Drug cue reactivity (Opioid Cues task)
- 3) Emotional identification (IDemo Task)
- 4)

Primary Hypothesis:

Aim 1 (Phase 1): Estimate the differential brain fMRI response between XRNTX and XRBUP in OUD treatment groups. We hypothesize that (**H1**) XRBUP and XRNTX will modulate the regional brain activity in the two-key cognitive-behavioral domains and measures of brain connectivity from pre-treatment (PRE) to on-treatment (ON) and this response will differ between the two medications. Milestone for transition to Phase 2: The MAT group (XRNTX, XRBUP) by Session (PRE, ON) **interaction** will have at least small ($d' \geq 0.2$) effect size in all brain measures.

H1a: Incentive salience (opioid cue-reactivity task): The decrease in the brain response to drug related stimuli (ON minus PRE) in the medial prefrontal cortex (mPFC) and the ventral striatum (VS) will be **greater** in the XRNTX than in the XRBUP group.

H1b: Executive function (Go-NoGo task): XRNTX will improve the efficiency of response inhibition more than XRBUP, leading to a greater **decrease** in the brain signal (ON vs PRE) during the NoGo trials in the inferior frontal cortex in the XRNTX group (see A.2.b).

H1c: Resting state functional connectivity (rsFC): change (ON vs PRE) in the rsFC between the VS and the right inferior frontal gyrus (rtIFG) and the mPFC will be **greater** in the XRNTX (vs. XRBUP group).

Aim 2 (Phase 2): Confirm in the full sample (n=200), the significance of MAT (XRNTX, XRBUP) by Session (PRE, ON) interaction in all domains from Aim 1. Test the explanatory value of integrated brain-behavior models of relapse vulnerability, identify differences in variable loading between MAT group, and explore potential mechanism of individual variability in treatment outcome.

H2a: Using logistic regression, we will test the explanatory value of brain signal in modeling treatment failure (Section **C.5.c**) and identify specific variables that differentiate MAT groups (interaction).

H2b (Exploratory): Test if the models that include brain response better explain treatment success or failure when compared to those fitted solely with demographic and clinical measures: demographic + clinical measures vs. demographic + clinical measures + brain response).

3.3 Secondary Study Endpoints (abbreviations spelled out on Page 27, “STUDY MEASURES”):

Depression (HAM-D2); Anxiety (HAM-A); Opioid Withdrawal (COWS); Opioid Craving (Opioid Craving Scale); TLFB interview; Percent UDS positive for cocaine (Ten-drug urine screen)

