4 STUDY PLAN

4.1 Study Design:

Single-blind, prospective study with Phase 1 (N = 60) to show feasibility and Phase 2 (N = 200) to confirm Phase 1 findings if they meet the milestones of effect size. This is to comply with the structure of the two-phase R61/R33 NIH funding mechanism. Both Phases will use the same sequence of data collection ([Section 3.1, Figure 2](#)).

Rationale for the study duration: Early medication effects are considered to be strong predictors of long term effectiveness both at the clinical (e.g. tolerability and symptom relief) and at the neural systems and pharmacodynamic levels (McDermott et al 2015). XRNTX exhibits high drop-out rate in the first 2 months of treatment, with 50% to 75% retention at the 3rd XRNTX injection (Wang et al 2015, Lee et al 2017). In a trial of sublingual buprenorphine, retention at 3 months was approximately 75% and relapse rates defined as repeated opioid positive urines were almost unchanged between 3 and 6 months time points (Lee et al 2017). Thus, a 70-day follow up period provided by two monthly XRNTX or XRBUP injections is a necessary and sufficient time window for a neurobiological evaluation of the mechanisms of relapse vulnerability while minimizing the effect of unrelated variables such as change in family, employment or medical status, on the outcome variable. We optimize the two-phase design by designing experiments that would generate data that could serve two purposes: the initial Phase 1 exploratory and milestone target and then part of the Phase 2 sample that would address confirmatory questions that require a sample size that neither phase could reach separately.

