4.4 End of Study Definition

A participant is considered to have completed the study if he or she has completed all phases of the study including the last visit or the last scheduled procedure shown in the Schedule of Activities (SoA), [Appendix Section 12.1](#). Proper referral and continuation of treatment after study discontinuation, with an option to continue the same medication for Vivitrol group and options to switch to oral preparation of buprenorphine or a biosimilar injectable extended release preparation that is available on the US market.. Participants will be offered referrals commensurate with their treatment preferences and the medication they received in the study. Individuals who drop out of study pharmacotherapy will be offered to continue their follow up visits. Individuals who drop out of study pharmacotherapy will be offered to continue their follow up visits. Participants completing the study will be referred to the clinical program of their choice using a “warm-handoff” procedure that will include (1) beginning to make arrangements for post-study referral before the effects of XRNTX or XRBUP wear off allowing one month for the project coordinator and the participant to establish clinical treatment (2) monitoring and assisting participants in making their follow up appointment and escorting them to their first appointment as needed (3) Providing psycho-education about opioid overdose risk and provide prescriptions for the nasal Naloxone spray used as a rescue in case of an overdose.

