7.2 Participant Discontinuation/Withdrawal from the Study

Participants are free to withdraw from participation in the study at any time upon request.

An investigator may discontinue or withdraw a participant from the study for the following reasons:

- Pregnancy
- Significant study intervention non-compliance
- If any clinical adverse event (AE), laboratory abnormality, or other medical condition or situation occurs such that continued participation in the study would not be in the best interest of the participant
- If the participant meets an exclusion criterion (either newly developed or not previously recognized) that precludes further study participation
- Participant missing a due injection for more than 14 days.

The reason for participant discontinuation or withdrawal from the study will be recorded on the study Case Report Form (CRF) along with a note to file. Subjects who sign the informed consent form and are randomized but do not receive the injection may be replaced. Subjects

who sign the informed consent form and are randomized and receive the injection, and subsequently withdraw, or are withdrawn or discontinued from the study, will not be replaced.

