7.3 Lost To Follow-Up

A participant will be considered lost to follow-up if he or she fails to return for more than 2 consecutive scheduled visits and is unable to be contacted by the study site staff.

The following actions must be taken if a participant fails to return to the clinic for a required study visit:

- The site will attempt to contact the participant and reschedule the missed visit and counsel the participant on the importance of maintaining the assigned visit schedule and ascertain if the participant wishes to and/or should continue in the study.
- Before a participant is deemed lost to follow-up, the investigator or designee will make every effort to regain contact with the participant (where possible, 3 telephone calls and, if necessary, a certified letter to the participant's last known mailing address or local equivalent methods). These contact attempts should be documented in the participant's medical record or study file.
- Should the participant continue to be unreachable, he or she will be considered to have withdrawn from the study with a primary reason of lost to follow-up.

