Effects of neural response on relapse vulnerability: Our primary outcome combines adherence to treatment and frequency of illicit opioid use during treatment. The primary outcome is a binary indicator of treatment success: if a patient provides ≥ 2 weekly UDS positive for opioids, or self-report of \geq two or more periods of ≥ 3 days of opioid use, or refuses XRNTX or XRBUP, or drops out of treatment entirely, then they will be classified as a treatment failure; otherwise they will be classified as a treatment success. We will calculate the PRE-ON change in %-signal-change for each of the regions and neural responses described in the R61 phase. We will use logistic regression models to predict the log-odds of treatment success (Aitkin et al 2009). The predictors in the model will be a binary factor for Group (XRNTX vs. XRBUP), and the neural change scores. We anticipate that there will be some greater PRE to ON changes in the XRNTX group than in the XRBUP group, so there will be some confounding between the effects of change score and the effects of Group on the rates of positive UDS. Thus, we will include Group first in our model, so evaluating the Group effect separate from the change-score effects, and then include the change scores in a model including Group, so evaluating the additional effect of change-scores in addition to the existing effects of Group. To assess whether the effects of the change scores differ between the XRNTX and XRBUP groups, we will also test for interaction effects between Group and each of the change-scores, by adding the interaction terms to the model that includes the group and neural change score main effects. We will check the assumptions underlying the logistic regression models (e.g. linearity of covariates effects on log-odds, outliers, influential observations) using standardized residuals, influence diagnostics, and graphical displays.

Sample size considerations for the sample: Analyses of Session by Group effects on neural response: For a one-sided test that the PRE vs ON effect is larger in the XRNTX group than in the XRBUP group, our sample of 70 per group yields 81% power for an effect of $d=0.42$ or greater. This effect is similar to the effects observed in the preliminary data. On the basis of the preliminary data we anticipate Group by Session effects of approximately $d=0.38$ in the VS and $d=0.42$ in the mOFC.

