13 APPENDIX

13.1 Schedule of Activities (SoA)

	Screening detox and randomization (Day -14)	MRI Scan 1 Baseline (day 0)	Induction to XRBUP or XRNTX (day 0-10)	Injection 1 (day 10) + weekly follow up	Injection 2 (day 40)	MRI Scan 2 On Treatment (day 55)	Injection 3 (Day 70)	Weekly Follow- up End of study and referral (Day 100)
Psychiatric and medical								
Demographics (age ¹ , sex ¹ , edu ¹)		X						
History, physical and labs (C.4.a)		X						
SILS		X						
MINI (EOS* – end of study)		X						X EOS*
Addiction Severity Index ¹		X						X EOS*
Clinical/Behavioral (C.3.a)								
HAM-D ² , HAM-A ² , COWS ²	X	X	X		X	X		X
SOWS, Opioid Craving Scale ² , SF-MPQ-2 ² , STAI-6		X	X	X	X	X		X
TLFB interview	X	X	X		X	X		X
Ten-drug urine drug screen (UDS)	X	X	X	X	X	X		X
Go-NoGo errors of commission ²		X		X				
Neuroimaging (Section C.3.b)								
Go-NoGo fMRI ³		X			X			
Opioid Cue task fMRI ³		X			X			
Resting-state fMRI ³		X			X			
MPRAGE (anatomical MRI scan)		X			X			

PRINCIPAL INVESTIGATOR SIGNATURE

STUDY SPONSOR: [name]

STUDY TITLE: **Open label comparison of injectable extended release preparations of buprenorphine (Brixadi®) and naltrexone (Vivitrol®) for the treatment of opioid use disorder**

STUDY ID 843403

PROTOCOL VERSION V5.0

I have read the referenced protocol. I agree to conduct the study in accordance to this protocol, in compliance with the Declaration of Helsinki, Good Clinical Practices (GCP), and all applicable regulatory requirements and guidelines.

Principal Investigator Name	[name]	Signature
Affiliation:	University of Pennsylvania	Date 7/17/2023

END OF DOCUMENT

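### The urine-screen endpoint in section 3.2 has no fixed window: read naturally, an early leaver with negative urines scores 0%, the same as an abstinent completer

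*Combined protocol and SAP*

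**What the plan says.** Section 3.2 gives two primary clinical endpoints. The first is the "percent of the urine drug screen (UDS) tests positive for opioids during the last month of participation". The second is a count of how many of the three injections the participant adhered to. The synopsis (section 1.1) uses the percentage of opioid-positive urines, with adherence, to define relapse, yet it lists urine toxicology among the secondary endpoints.

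Section 9.1 uses a different clinical outcome, a binary treatment failure. A participant who meets a positive-urine or self-report criterion, refuses the injection, "or drops out of treatment entirely, then they will be classified as a treatment failure".

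Several passages bear on when participation ends:

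- Section 7.2 lets the investigator withdraw a participant for reasons that include "Participant missing a due injection for more than 14 days".
- Section 7.3 says of someone who stays unreachable that "he or she will be considered to have withdrawn from the study with a primary reason of lost to follow-up".
- Section 4.4 says "Individuals who drop out of study pharmacotherapy will be offered to continue their follow up visits", and section 3.4 encourages those discontinued from the trial to attend follow-up.

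The timetables differ:

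- The synopsis gives a participant duration of 20 weeks.
- Section 3.1 describes up to 30 days of screening and baseline, a 12-week medication phase "and one follow-up visit 4 weeks after end of medication phase".
- Section 4.1 speaks of a 70-day follow-up from two monthly injections.
- Section 4.2 speaks of outcomes at 2 months.
- Section 6.4 lists observed injections on days 10 and 40.
- The Schedule of Activities (13.1) has injections on days 10, 40 and 70, with weekly follow-up to day 100.

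**The concern.** If the month is counted back from each person's own exit, leaving the study after a run of negative urines fixes the score at its best value. People are also compared over different parts of the study: an early leaver just after detoxification and the first injection, a completer at the end. The same early leaver is abstinent on the section 3.2 percentage and a failure under section 9.1.

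The missing-data methods in sections 9.1 and 9.4.1 would not catch this. They address weekly or longitudinal use records. A percentage anchored to exit looks complete for an early leaver, so nothing is flagged as missing.

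Retention may differ by arm. Section 4.1 expects high early drop-out on XRNTX, "with 50% to 75% retention at the 3rd XRNTX injection", and cites about 75% at 3 months for sublingual buprenorphine. It gives no figure for XRBUP. A descriptive comparison of the arms on this endpoint could therefore be shifted by who leaves.

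**Working it through.** The plan states no effect size, power or denominator for this endpoint, so there is no figure to reproduce. The check applies the definition to individuals and then to arm averages.

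**Individuals** (Schedule of Activities days, weekly urines, a month taken as 30 days)

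- Leaver: injected on day 10, negative on days 17, 24, 31 and 38, exits at day 40. The window is days 10 to 40 and the score is 0/4 = 0%.
- Participant withdrawn under section 7.2 for the day-40 injection: earliest exit is after day 40 + 14 = 54. The window is about days 24 to 54.
- Abstinent completer: exits at day 100. The window is days 70 to 100 and the score is 0%.
- Completer on the section 3.1 timetable: the last month is the 4 weeks after the medication phase, for which that section schedules one visit.

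**Timetables.** Section 3.1 adds up to 30 + 84 + 28 = 142 days, close to the synopsis's 20 × 7 = 140. The Schedule of Activities runs from day -14 to day 100, or 114 days. So even reading the endpoint as the last scheduled month does not give a single window or test count.

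**Arm averages (illustration only).** Arm mean = r·c + (1 - r)·x, where r is retention, c the completers' positive rate and x the rate assigned to leavers. Retention is r = 0.50 for XRNTX (the low end of section 4.1's range) and r = 0.75 for XRBUP (borrowed from sublingual buprenorphine). The value c = 0.20 and all values of x are assumptions. Everyone not retained is taken to leave the study entirely.

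| Scoring | x | XRNTX | XRBUP | Difference (points) |
|---|---|---|---|---|
| Own-exit window | 0 | 10% | 15% | -5 |
| Own-exit window | 0.20 | 20% | 20% | 0 |
| Own-exit window | 0.40 | 30% | 25% | +5 |
| Fixed window, missed tests positive | 1 | 60% | 40% | +20 |
| Fixed window, leavers half positive | 0.50 | 35% | 27.5% | +7.5 |
| Fixed window, leavers like completers | 0.20 | 20% | 20% | 0 |

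For example, the third row is 0.50 × 0.20 + 0.50 × 0.40 = 0.30 against 0.75 × 0.20 + 0.25 × 0.40 = 0.25.

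With a pre-exit rate q common to both arms, moving to a fixed window with missed tests counted positive shifts the difference by (r_XRBUP - r_XRNTX)·(1 - q):

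- q = 0: 0.25 × 1 = 25 points
- q = 0.20: 0.25 × 0.80 = 20 points
- q = 0.40: 0.25 × 0.60 = 15 points

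Three variations:

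- If only half of those not retained leave entirely, the 25-point shift halves to 12.5.
- With c = 0.40, the own-exit differences are -10, -5 and 0 points for the same three values of q, against +15 in the fixed window with missed tests positive.
- With 75% retention in both arms and equal q, the shift is 0. The levels still change: with c = 0.20 and q = 0, each arm rises from 15% to 40%.

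**The case against.** **No planned analysis is touched.** No model in section 9 uses this percentage. The fMRI interaction tests, the binary outcome behind H2a and H2b, and the GEE analyses of weekly use are unaffected, and those GEE analyses have their own missing-data sensitivity analyses. This stands. A reader might infer that the trial's main inference is compromised, but the documents do not support that.

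**The paired endpoint separates the two people.** The injection count gives the leaver 1 and the completer 3. This stands as a limit on the harm, but it does not correct the urine score, which is listed as an endpoint in its own right.

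**Participation might mean the scheduled period.** The synopsis gives a fixed duration, and section 3.2 points to the Schedule of Activities. The reading is possible, so the own-exit window is the natural reading and not a settled fact. However, no passage states the fixed reading, and the timetables it would rely on disagree.

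**Leaving treatment need not mean leaving the study.** Those who stop drug may keep attending, and withdrawal under section 7.2 is discretionary. This stands. Whether urines from such visits count is not stated.

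**The reversal is a corner case.** A reader might infer from -5 against +20 that the endpoint would reverse the arm comparison. That needs leavers with no positive urines before exit, every missed test positive, the lowest XRNTX retention and a borrowed XRBUP figure. Section 2.2 places continued illicit use on a continuum with non-adherence, which argues against assuming no positives before exit. At 40% positive before exit the sign does not change.

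**Conclusion.** The concern holds in a limited form. The endpoint's window and denominator are undefined. On the natural reading, exit after negative urines scores the same as abstinence to the end, and section 9.1 calls the same person a failure. That part follows from the wording and needs no assumed rates.

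The size and direction of any distortion between arms are not established. In the illustration the own-exit difference runs from -5 to +5 points, against +20 with a fixed window and missed tests counted positive. It does not shift when retention and leaver rates are equal. The completers' and leavers' positive rates and XRBUP retention are assumptions.

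The endpoint's standing is also inconsistent, since section 3.2 makes it primary and the synopsis makes urine toxicology secondary. It should be fixed before analysis because the choice of window can change the result, but it does not threaten the planned fMRI or treatment-failure analyses.

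A minor related gap is that opioid-positive is not defined by analyte, while the urine panel in sections 6.1 and 8 includes buprenorphine, the XRBUP study drug. A reader might infer that study drug would be scored as use. Section 9.1's reference to illicit use and section 9.4.1's use of urine screens to measure compliance point the other way, but no scoring rule says so.

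**What to change.** - Replace the current window with one fixed in study days for all participants, after reconciling the timing statements in the synopsis, sections 3.1, 4.1, 4.2 and 6.4, and the Schedule of Activities.
- Use the tests scheduled in that window as the denominator.
- State that urines from follow-up visits after stopping study drug count if they fall in the window.
- Pre-specify how tests missed after exit are handled, with sensitivity analyses under alternatives. Counting them positive is one option. It partly overlaps the adherence endpoint, and section 9.1's failure rule does not itself require it.
- Reconcile the endpoint's primary or secondary status between section 3.2 and the synopsis, and state how it relates to the section 9.1 outcome.
- Name the analytes that count as opioid-positive, the same in both arms, and state that study-drug buprenorphine is not scored as positive. Dropping buprenorphine from the score would hide non-study use in the XRNTX arm, so report it separately by arm.

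The cost is protocol and SAP wording and a little extra analysis. No new data are needed.
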